1.4. Synopsis

Title of the clinical investigation	Performance and safety assessment of T4020 combined with standard post-operative therapy versus standard post-operative therapy in managing corneal epithelial defect following epi-off accelerated corneal crosslinking
International Coordinating Investigator	Prof (Associate) [name], Kayseri (Turkey)
Clinical investigation design	This is a prospective, randomised, double-masked, controlled, multicentre international clinical investigation
Clinical investigation objective(s)	
Primary objective: To assess performance of T4020 combined with standard post-operative therapy versus standard post-operative therapy regarding corneal epithelial defect (CED) healing following epi-off accelerated corneal crosslinking (CXL)
 
Other objectives: To assess ocular symptoms and safety

Clinical investigation endpoints	
Primary performance endpoint: Response defined as complete healing of CED (absence of CED) as assessed by the investigator on Corneal Fluorescein Staining (CFS) at slit lamp examination. (A patient with complete healing of CED could still present superficial punctate keratitis [SPK] or stained healing lines). Two time points will be considered: Day 3 (D3) and Day 4 (D4).
 
Secondary performance endpoint:
 
 - CED size assessed by the investigator on CFS at slit lamp examination after Contact Lens (CL) removal at D3, D4, and D5. 
Other performance endpoints:
 
 - Time to complete healing of CED. - Superficial punctate keratitis (SPK) (graded using the National Eye Institute [NEI] 0 - 15 scale) at D3, D4 and D5. - Presence or absence of stained typical healing lines at D3, D4 and D5. - Conjunctival staining (graded using the National Eye Institute [NEI] 0 - 18 scale) at screening visit and D5. - Total ocular pain score (graded on 0-10 Numeric Rating Scale) at D1, D2, D3, D4, and D5. - Each symptom including light sensitivity, burning / stinging, tearing, foreign body sensation (graded on 0-10 numeric rating scale: 0: absence of the symptom and 10: worst imaginable symptom) at D1, D2, D3, D4, and D5. - Sum of scores of light sensitivity, burning / stinging, tearing, foreign body

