	
sensation at D1, D2, D3, D4 and D5.
 
 - Use of painkillers at D1, D2, D3, D4 and D5. - Measurement of the CED on CFS photos by a reading center at D1, D3, D4, and D5 (ancillary). 
Safety endpoints:
 
 - Conjunctival hyperaemia (graded using the McMonnies grading [0 to 5]) at D3, D4 and D5. - Uncorrected visual acuity (UCVA) and far best corrected visual acuity (BCVA) (using a Snellen chart) at screening visit and D5 after CL removal. - Non-contact intraocular pressure (IOP) at screening visit and D5 (after CL removal). - Adverse events (AEs)/ Adverse Device Effects (ADEs) recorded throughout the clinical investigation by the investigator.
Investigational Product	
T4020 will be combined with the standard post-operative therapy.
 
Dosing regimen: one administration into the CXL eye every other day for 5 days:
 
 • The first one at surgery before fitting CL, • The second one at D3 (after the visit, on the CL) at the site, • The third one at D5 (in the morning at home before the visit, on the CL). 
Saline solution will be combined with the standard post-operative therapy.
 
Dosing regimen: one administration into the CXL eye every other day for 5 days:
 
 • The first one at surgery before fitting CL, • The second one at D3 (after the visit, on the CL) at the site, • The third one at D5 (in the morning at home before the visit, on the CL).

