	
All randomised patients having received at least one dose of investigational product and with at least one post-baseline performance assessment on product.
 
Per protocol (PP) set: All mITT patients without any major clinical investigation plan violation.
 
Safety endpoints will be analysed in the safety set. Performance endpoints will be primarily analysed in the mITT set.
 
Baseline: The baseline visit is the inclusion visit (D1) for all assessments.
 
Sample size: The principal statistical hypothesis is the superiority of T4020 compared to control for the primary efficacy variable. The sample size determination is based on the primary efficacy endpoint, i.e. the response defined as complete healing of CED (absence of CED) in the eye undergoing CXL as assessed by the investigator on Corneal Fluorescein Staining (CFS) at slit lamp examination at Day 3 (D3) and Day 4 (D4) using the Hochberg procedure for multiple testing. Using this step-up procedure, unadjusted p-values are ordered from the largest (p1) to the smallest (p2). If the largest p-value (p1) is lower than 0.05, both null hypotheses can be rejected at the overall 5%-level of significance. If the largest p-value (p1) is greater than 0.05 and the smallest p-value (p2) lower than 0.025, only the null hypothesis corresponding to p2 can be rejected at the overall 5%-level of significance. Bases on estimated response rates of 60% in the T4020 group and 30% in the control group, 132 evaluable patients (66 per group) are needed to achieve at least 90% power using a two-sided 0.025 significant nominal level.
 
Interim analysis: No interim analysis is planned.

Planned schedule	
Planned initiation of the clinical investigation: September 2016 Planned completion date of the clinical investigation: June 2017

FLOW CHART: Clinical investigations are to be conducted as per the following schedule of investigation procedures:

Clinical investigation procedure	Screening Within 60 Days [D] before D1	Visit D1				Visit D2 = 24h (± 2h) ^(a)	Visit D3 = 48h (± 2h)	Visit D4 = 72h (± 2h)	Final Visit D5 = 96h (± 2h) ⁽ⁿ⁾
		Pre-op.	Intra-op.	Post-op.	Phone call 4 hours post- op. ^(a)				
Informed consent	X								
Demography / Smoking status	X								
Keratoconus (KC) history	X								
Ocular medical and surgical history	X								
Ocular surface disease index (OSDI)	X								X
Systemic medical and surgical history	X								
Verification of inclusion and exclusion criteria	X	X							

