Previous and concomitant ocular/non ocular products	X	X				X	X	X	X
Patient diary :									
- Painkiller(s) use ^(b)		X ^(c)		X	X	X	X	X	X
- Ocular pain assessment (Numeric Rating Scale, NRS)	X ^(c)	X ^(c)		X	X ^(d)	X ^(e)	X ^(e)	X ^(e)	X ^(e)
Ocular symptoms ^(f)					X	X	X	X	X
Corneal topography with pachymetry	X								
Far Uncorrected and Best Corrected Visual acuity (UCVA and BCVA) with manifest refraction	X								X
Slit-lamp examination ^(g)	X	X					X	X	X
Tear Break-up time (TBUT) with fluorescein	X								
Corneal fluorescein staining with CED assessment and photos (blue light) ^(h)	X						X	X	X
Conjunctival staining with lissamine green	X								X
Conjunctival hyperaemia							X	X	X
Corneal sensitivity assessment (by the Cochet-Bonnet aesthesiometer)	X								
Peri-operative pachymetry			X						

Clinical investigation procedure	Screening Within 60 Days [D] before D1	Visit D1				Visit D2= 24h ($\pm 2h$) ^(a)	Visit D3 = 48h ($\pm 2h$)	Visit D4 = 72h ($\pm 2h$)	Final Visit D5 = 96h ($\pm 2h$) ^(o)
		Pre-op.	Intra-op.	Post-op.	Phone call 4 hours post- op. ^(a)				
Intraocular pressure (IOP) measurement on both eyes (non-contact tonometry)	X								X ⁽ⁱ⁾
Schirmer test with anaesthesia	X								
Surgery: epi-off corneal collagen cross-linking (CXL) procedure			X						
Randomisation		X							
Investigational product instillation			X ^(j)				X ^(k)		X ^(l)
Contact lens (CL) insertion ^(m)			X				X	X	
Peri-operative photos				X					
Urinary pregnancy test ⁽ⁿ⁾	X								
Adverse Event(s) (AE) / Adverse Device Effect(s) (ADEs) collection		X	X	X	X	X	X	X	X

^(a) A phone call will be performed 4 hours after the CXL procedure by the investigator/delegate to collect the ocular symptoms and to remind the patient to complete the diary. Visit D2 will be also a phone call done by the investigator/delegate.

^(b) Number of painkiller(s) pills recorded by the patient in the patient diary will be collected. The 1st administration of the painkiller (Paracetamol 1g) will be done 1 hour after CXL. The 2nd administration will be at least 4 hours later and no more than 4 times daily. In case of real severe pain, patient can take Paracetamol 500mg with 30mg Codein instead of Paracetamol 1g, not exceeding 4 tablets/day (including tablets with paracetamol and tablets with paracetamol/codein).

^(c) For training purposes.

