^(d) The patient should be instructed to note the NRS pain score 1 hour after CXL procedure before the 1st painkiller administration, then 3, 6 and 12 hours after CXL procedure and before painkiller administration.

^(e) The patient should be instructed to note the NRS pain score at wake up time(8:00 am +/- 2h), midday (2:00 pm +/- 2h) and bedtime (8:00 pm +/- 2h) and before painkiller administration.

^(f) Ocular symptoms (light sensitivity, burning/stinging, tearing, foreign body sensation) will be collected by the investigator/delegate.

^(g) Slit lamp examination: any clinically relevant finding will be recorded.

^(h) The CED will be measured with caliper / with the slit lamp after contact lens (CL) removal if applicable.

⁽ⁱ⁾ IOP at visit D5 if complete healing.

^(j) The investigational product will be instilled by the medical staff before CL insertion at the end of the CXL procedure at visit D1.

^(k) The investigational product will be instilled by the medical staff after CL insertion at Visit D3.

^(l) The investigational product will be instilled by the patient (on the CL) in the morning D5 before the Visit.

^(m) The removal of the CL will be done with forceps after hydration before ocular examination and a new CL will be used at visit D3 and visit D4.

⁽ⁿ⁾ Women of child bearing potential must have a negative urinary pregnancy test prior to the initial instillation of investigational product.

^(o) Follow up of the patient can be done if complete healing isn't reached, according to the investigator judgement. All procedures will be performed as scheduled for the final visit D5.

Op.: Operatively

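### No McMonnies hyperaemia grade is scheduled before treatment, so graded worsening cannot be derived and the arm comparison cannot be adjusted for baseline redness (a low-severity, secondary safety point)

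*Combined protocol and SAP*

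**What the plan says.** The safety endpoints in the synopsis (section 1.4) include "Conjunctival hyperaemia (graded using the McMonnies grading [0 to 5]) at D3, D4 and D5". The flow-chart row "Conjunctival hyperaemia" agrees: it is marked at D3, D4 and D5 and blank at screening, at every D1 column and at D2. The investigational product is first given at surgery on D1, so no grade precedes treatment.

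The statistical part of the synopsis states: "The baseline visit is the inclusion visit (D1) for all assessments".

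The other measured safety endpoints each have a value before surgery. Pressure, for example, is listed as "Non-contact intraocular pressure (IOP) at screening visit and D5 (after CL removal"), and visual acuity follows the same two visits.

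The flow chart also marks "Slit-lamp examination" at screening and at D1 pre-op. Its note (g) reads: "Slit lamp examination: any clinically relevant finding will be recorded". No hyperaemia grade is attached to those two examinations.

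**The concern.** Redness graded 2 at D3 may be the patient's usual state or something new. Without an earlier grade on the same scale, the size of any change is unknown. Safety is a stated objective, and hyperaemia is the only sign in the safety list graded at three post-operative visits. Adverse events and device effects are collected from D1 pre-op onwards, so an investigator judging whether redness at D3 to D5 is an event has no graded reference for that eye.

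The baseline rule makes this more than a matter of taste, because it covers all assessments and this one has no D1 value. Visual acuity and pressure have no D1 value either, but reading baseline as screening would settle them. No redefinition can settle hyperaemia, since there is no earlier grade to point to. The remedy has to be a measurement, and a patient's pre-treatment grade cannot be recovered once that patient has been treated.

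**Working it through.** **Schedule, side by side** (synopsis endpoint lists, exclusion criteria and flow chart)

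| Assessment | Before treatment | After treatment |
|---|---|---|
| Hyperaemia, McMonnies 0 to 5 (safety) | none | D3, D4, D5 |
| Visual acuity (safety) | screening | D5 |
| Intraocular pressure (safety) | screening | D5 |
| Conjunctival staining, NEI 0 to 18 (performance) | screening | D5 |
| Corneal staining / SPK, NEI (performance) | staining at screening | D3, D4, D5 |
| Slit-lamp findings, ungraded | screening, D1 pre-op | D3, D4, D5 |

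SPK is the nearest comparison, as it is listed for the same three visits: "Superficial punctate keratitis (SPK) (graded using the National Eye Institute [NEI] 0 - 15 scale) at D3, D4 and D5". It is a performance endpoint, however. The flow chart also marks corneal fluorescein staining at screening, and exclusion 2.1.5 needs an NEI score there. Hyperaemia is the only safety endpoint on a scale with nothing before treatment.

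**Arm size.** The plan's figure reproduces. Inputs: response rates 60% and 30%, two-sided 0.025, 90% power. With pooled variance under the null and no continuity correction:

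n = [2.241 × √(2 × 0.45 × 0.55) + 1.282 × √(0.6 × 0.4 + 0.3 × 0.7)]² / 0.30² ≈ 66 per arm, 132 in all.

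This supplies only the 66 used below; the point does not depend on it.

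**Precision of the hyperaemia comparison.** The documents give neither an SD nor a pre/post correlation r for this grade. Results are therefore in SD units and r is an assumed range. The grade is treated as approximately continuous.

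- Standard error of the arm difference: √(2/66) = 0.174 SD.
- Unadjusted 95% half-width: 1.96 × 0.174 = 0.341 SD.
- Adjusted half-width: 0.341 × √(1 − r²).
- Equivalent extra patients for this endpoint: 1/(1 − r²) − 1.

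| Assumed r | Variance factor 1 − r² | Adjusted half-width (SD) | Equivalent extra patients |
|---|---|---|---|
| 0.1 | 0.99 | 0.339 | 1% |
| 0.3 | 0.91 | 0.325 | 10% |
| 0.5 | 0.75 | 0.295 | 33% |
| 0.6 | 0.64 | 0.273 | 56% |

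**Chance imbalance.** The probability that the arms differ before treatment by more than 0.25 SD (a threshold chosen for illustration) is 2 × [1 − Φ(0.25/0.174)] = 0.15. An imbalance of exactly that size would shift the post-operative comparison by r × 0.25: 0.025 SD at r = 0.1, 0.075 SD at 0.3 and 0.15 SD at 0.6. All are below the 0.341 SD half-width. This is not a further cost, because the unadjusted interval already allows for it.

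**The case against.** The strongest reply is that comparing post-operative grades by arm is a legitimate design. Randomisation and masking protect it, and the saline arm, not a baseline grade, separates product-related from surgery-related redness. That stands. A reader might infer that the hyperaemia comparison is biased or uninterpretable; the documents do not support that.

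A reader might also infer that pre-existing redness goes entirely unrecorded. Note (g) contradicts this: marked redness at screening or D1 pre-op should appear as a clinically relevant finding. What remains is that such an entry is ungraded and depends on the examiner's view of relevance, so it cannot feed a shift table or serve as a covariate on the 0 to 5 scale.

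Eligibility also narrows the range of pre-treatment redness. The exclusions cover OSDI above 23, Schirmer below 10 mm/5 min, TBUT below 7 seconds, corneal or conjunctival staining above 3, recent or active infection, a history of atopic keratoconjunctivitis, and active uveitis. None of the criteria shown caps hyperaemia itself, but together they remove many inflamed or dry eyes and probably reduce what a baseline covariate would add.

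Epi-off crosslinking, peri-operative drops and a bandage lens also come between any baseline and D3. If they drive redness, r is low and the precision argument nearly vanishes.

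Finally, the available text does not show how hyperaemia will be analysed, and nothing in it promises change from baseline. The case therefore rests on the plan's own baseline rule and on patient-level interpretation, not on a broken analysis commitment.

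**Conclusion.** The point holds as a low-severity, secondary safety matter. The synopsis and flow chart agree that no McMonnies grade precedes treatment, so the D1 baseline rule cannot be met for this endpoint. For patients with redness at D3 to D5, change, shift and graded worsening cannot be derived, and the arm comparison cannot be adjusted for baseline grade. This patient-level loss does not depend on any assumed correlation.

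The precision loss does. Over assumed r of 0.1 to 0.6, adjustment would bring the half-width from 0.341 SD to between 0.339 and 0.273 SD, with the smallest gain if surgery dominates.

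It would go too far to say that emergent hyperaemia is unidentifiable in every patient, since one graded 0 at D3, D4 and D5 has none at those visits. The primary and secondary endpoints, the sample size and the error rate are unaffected.

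**What to change.** Mark the hyperaemia row of the flow chart at D1 pre-op and take the McMonnies grade at the slit-lamp examination already scheduled there, before any peri-operative drop. If that is not practical, take it at the screening slit-lamp examination and name screening as the baseline for this endpoint; screening can be up to 60 days earlier, so D1 is preferable. Add the visit to the endpoint list, tabulate shifts from that grade to D3, D4 and D5 by arm, and adjust the arm comparison for it.

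The cost is one extra CRF field to complete and monitor and about a minute per patient, with no new visit, instrument or staff. The change needs to be in place before patients are treated.

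If the sponsor prefers not to add the grade, the plan should state that hyperaemia is analysed on post-operative values only and exempt it from the D1 baseline rule.

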Methodology	
Randomisation:
 
Patients will be randomised into two groups. In one group, T4020 will be used and, in the other group, saline solution will be used.
 
Auxiliary products and Therapies:
 
During the perioperative period, clinical investigation personnel will instil the drops. Then, the patients will instil the drops after they go home. All participants will be asked to use the same medications before and after the procedure as scheduled in the clinical investigation plan and detailed in the investigator manual:
 
In addition to cutaneous anti-infective solution and the bandage contact lens, the standardised treatment will include topical anaesthetic, direct-acting cholinergic agonist, topical antibiotic and artificial tears. Topical corticosteroid will be started after complete corneal healing.
 
Epi-off accelerated cross-linking with isotonic riboflavin will be performed as detailed in the protocol.
 
Patients will be permitted to take oral paracetamol 1g for ocular pain and

	paracetamol 500mg with codein 30mg or equivalent in case of severe pain.																									
Number of patients	About 147 screened patients to obtain 132 evaluable patients.																									

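### Does planning for about 147 screened patients leave the trial short of the 132 evaluable patients behind its 90% power?

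*Combined protocol and SAP*

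**What the plan says.** The Synopsis row on the number of patients reads "About 147 screened patients to obtain 132 evaluable patients".

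The Synopsis paragraph on sample size gives the basis for the 132. It assumes response rates of 60% on T4020 and 30% on control, and says that "132 evaluable patients (66 per group) are needed to achieve at least 90% power using a two-sided 0.025 significant nominal level". The nominal 0.025 comes from testing response "at Day 3 (D3) and Day 4 (D4) using the Hochberg procedure for multiple testing".

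On the analysis population, the Synopsis says "Performance endpoints will be primarily analysed in the mITT set". A randomised patient enters that set after one dose, "with at least one post-baseline performance assessment on product".

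The flow chart allows screening up to 60 days before D1. It lists "Verification of inclusion and exclusion criteria" both at screening and pre-operatively at D1. Randomisation is at D1 before surgery, the first dose is given by staff at the end of the same procedure, and the final scheduled visit is at 96 hours.

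The available text is the synopsis and flow chart. It states no screen-failure rate, no dropout rate, no number to randomise, no definition of an evaluable patient, and no rule on whether screening continues until the target is met.

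**The concern.** Inflating an evaluable number by 10% is the usual way to get from patients analysed to patients randomised. Here the inflated figure is attached to patients screened, which is an earlier and larger pool. Screening in this trial is a genuine filter: keratoconus stage, corneal thickness, corneal sensitivity, OSDI, Schirmer, TBUT, corneal and conjunctival staining and BCVA all carry cut-offs, and there is a long list of excluded prior treatments. Most of these tests are done at the screening visit, so a patient counts as screened before the results are known.

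If one 10% allowance has to absorb both screen failures and later losses, the evaluable number could fall below 132. On the plan's formula 66 per group is the smallest number that reaches 90%, so any shortfall takes the stated power below its target.

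**Working it through.** **Inputs.** From the Synopsis: p1 = 0.60, p2 = 0.30, two-sided nominal level 0.025, power 0.90, equal groups, 132 evaluable, about 147 screened. Attrition rates are not given, so those below are assumptions.

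**1. The plan's own figure.** Normal approximation with pooled variance under the null, where the mean rate is 0.45:

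n per group = [z(0.9875)·√(2·0.45·0.55) + z(0.90)·√(0.60·0.40 + 0.30·0.70)]² / 0.30²

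= [2.2414·0.7036 + 1.2816·0.6708]² / 0.09 = (1.5770 + 0.8597)² / 0.09 = 65.97, so 66 per group and 132 in total. Power is 90.01% at 66 per group and 89.5% at 65. The 132 reproduces.

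**2. Where 147 comes from.** 132/0.90 = 146.7, rounded up to 147. The margin is 147 − 132 = 15 patients, and 15/147 = 10.2%. There is no arithmetic error.

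**3. What happens if screening stops at exactly 147.** Evaluable N = 147·(1 − screen failure)·(1 − later loss). Power is for one time point at nominal 0.025. Screened needed = 132/[(1 − screen failure)·(1 − later loss)], rounded up.

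| Screen failure (assumed) | Later loss (assumed) | Evaluable from 147 | Power | Screened needed for 132 |
|---|---|---|---|---|
| 0% | 10% | 132.3 | 90.1% | 147 |
| 5% | 5% | 132.7 | 90.2% | 147 |
| 10% | 0% | 132.3 | 90.1% | 147 |
| 10% | 5% | 125.7 | 88.4% | 155 |
| 15% | 0% | 125.0 | 88.2% | 156 |
| 10% | 10% | 119.1 | 86.4% | 163 |
| 20% | 10% | 105.8 | 81.7% | 184 |
| 30% | 10% | 92.6 | 75.6% | 210 |

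Under such a cap, the chance of at least 132 evaluable from 147 is 60% if each screened patient has a 90% chance of being evaluable, and 6% if that chance is 85%.

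**4. What happens if recruitment runs to 132 evaluable.** Power stays at 90.0% in every row. Only the last column changes, and it is a forecast of effort.

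**5. How much later loss to expect.** Randomisation, surgery and the first dose fall on the same day, and follow-up lasts four days. One post-baseline performance assessment keeps a dosed patient in the mITT set, and pain and symptom scores from the first two days are among the performance endpoints. A patient can still miss the D3 or D4 healing assessment, but a 10% loss after randomisation on top of screen failure is at the pessimistic end.

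**6. The 90% is for one time point.** The Hochberg rule also rejects both hypotheses when the larger p-value is below 0.05. If 60% versus 30% holds on both days (an assumption; the plan gives one pair of rates without naming a day), a bivariate normal simulation with correlations from 0.3 to 0.999 puts the power to reject at least one hypothesis at about 94% to 98% with 132 patients, and about 92% to 97% with 119. If the effect exists on one day only, the figures in the table stand approximately.

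**The case for a change.** The best case for a change is that screening losses alone could use up the margin. Short follow-up and a lenient mITT rule do nothing about patients who fail the tear-film, OSDI or staining thresholds, and 15% screen failure with no later loss already brings 147 down to 125. If 147 is only a forecast, it still rests on an unstated rate, and nothing in the available text says that screening continues until the target is met. Stating the number to randomise, the assumed rates and a continuation rule would cost a few lines.

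Part of this stands. The allowance is about 10% from screening onward, it is not justified, and those details are absent from the text at hand. It does not show that the evaluable number will be missed. The screen-failure rate is unknown in both directions: the inclusion criteria require patients already scheduled for epi-off crosslinking, which may limit failures, while the measured thresholds may add to them. Replacing 147 screened with 147 randomised would guess at what the authors meant. Nor can the absence of a recruitment rule from a synopsis and flow chart establish that the trial has none.

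**Conclusion.** The concern does not call for a change. The 132 and its 90.0% power are correct, and 147 is a correct 10% inflation of it. A shortfall needs two things that the documents do not state: combined attrition above 10.2%, and screening that ends at 147. The wording points away from the second, because the count is approximate and 132 evaluable is what it is meant to achieve.

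If both held, moderate excess attrition would cost a few points of single-time-point power: 88.4% at 10% plus 5%, and 86.4% at 10% plus 10%. Among the rows tabulated, power falls below 80% only at 30% plus 10%. If recruitment simply runs to the evaluable target, the loss is nil and the cost is more screening.

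The missing attrition rates, number to randomise and continuation rule are a gap in recruitment detail that a trial team fills sensibly in the ordinary course of work. They do not alter the endpoint, the analysis or the required number. This conclusion assumes that 132 evaluable is the recruitment goal; a firm ceiling of 147 screened, if one were stated elsewhere, would reopen the question.
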